3.1.1. Part A: Placebo-Controlled Treatment Period

Part A of Study 1821-FSH-301 is a global, randomized, double-blind, placebo-controlled, parallel-group, multicenter study with a [REDACTED] screening period, a 48-week treatment period, and safety follow-up visits [REDACTED] days and [REDACTED] days after last dose (for patients who discontinue from treatment early or who do not rollover into Part B).

During the placebo-controlled treatment period, a total of approximately 230 patients with FSHD will be randomized 1:1 to receive 15 mg PO of losmapimod (n=115) or placebo (n=115) tablets BID with food for 48 weeks (Figure 1).

Patients will complete a [REDACTED] screening period followed by a 48-week placebo-controlled treatment period. After Week 48 patients will have the option to participate in Part B: Open-Label Extension (Section 3.1.2).

- Patients will have the opportunity to rollover into Part B after completing Part A. Approval from the Medical Monitor will be required if patients do not rollover without interruption after completing the Week 48 assessments. If a patient rolls over more than 7 days after the last dose in Part A, they may be required to repeat selected Week 48 assessments at the discretion of the Medical Monitor.
- For patients who rollover into Part B, the Week 48 visit will be the end of study visit for Part A.
- All patients who discontinue from treatment early or who do not rollover into Part B will return for a complete safety follow-up visit [REDACTED] days after the last dose of study drug and will complete a safety follow-up phone screen [REDACTED] days after the last dose of study drug.

During the treatment period, patients will be asked to attend the study clinic at each scheduled visit (Table 7).

Safety and tolerability will be evaluated based on the assessment of AEs, AEs of special interest (AESIs), SAEs, laboratory tests, ECGs, vital signs, and physical examinations. The full schedule of assessments for the placebo-controlled treatment period is provided in [Table 7](#). Scheduled visits may be split over 2 days, if required, and must be completed within the protocol-defined visit windows ([Table 7](#)). Unscheduled visits may be performed if clinically indicated.

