3.1.2. Part B: Open-Label Extension

Upon completion of Part A at Week 48, patients will have the option to rollover into Part B, the open-label extension ([Figure 1](#)). Patients should be prepared to rollover into Part B as soon as possible after the last dose of study drug in Part A (Week 48 visit). Approval from the Medical Monitor will be required if patients do not rollover without interruption after completing the Week 48 assessments. If a patient does not rollover within 7 days of the last dose of study drug in Part A, they may be required to repeat selected Week 48 assessments (at the discretion of the Medical Monitor) to establish baseline for Part B. Study drug will not be administered in Part B until all assessments for Part A have been completed.

As outlined in [Table 8](#), the Day 1 visit of Part B (baseline) may occur on the same day as the Week 48 visit of Part A. If the patient rolls over within 7 days of the Week 48 visit, the Week 48 assessments will not be repeated at the beginning of Part B. Patients will provide informed consent before any Part B-specific assessments are performed.

Patients will remain blinded to their Part A treatment assignment (losmapimod or placebo) through completion of Part B. During Part B, all patients will receive 15 mg PO losmapimod tablets BID with food. Patients may continue to receive study drug in Part B for the duration of the study as specified in the visit schedule ([Table 8](#)) or until the study is discontinued by the sponsor. Any planned treatment interruptions (e.g., scheduled surgery) during Part B may be permitted on a case-by-case basis with approval from the Medical Monitor.

Part B will consist of in-person clinic visits at baseline (Week 48) and at Weeks [REDACTED] [REDACTED]. After the [REDACTED] visit and for the remainder of the study, in-person clinic visits will occur [REDACTED] [REDACTED]. All patients who complete or discontinue from treatment will return for a complete safety follow-up visit [REDACTED] days after the last dose of study drug and will complete a safety follow-up phone call [REDACTED] days after the last dose of study drug.

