9.1.6.7. Safety Analyses

Safety data in the placebo-controlled treatment period will be analyzed using the safety analysis set and summarized by treatment group and visit (if applicable) using descriptive statistics.

Treatment-emergent AEs will be summarized by MedDRA system organ class and preferred term; separate summaries will be produced for treatment-related AEs, AESIs, SAEs, and discontinuations due to AEs. Laboratory tests, vital signs, findings from physical examinations, and ECGs will be summarized for changes over time during treatment using descriptive statistics.

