Abbreviations: BMI = body mass index; ECG = electrocardiogram; █; FSHD = facioscapulohumeral muscular dystrophy; F/U = follow-up; ICF = informed consent form; PRO = patient-reported outcome; RWS = reachable workspace.

^a In most cases, the baseline visit of Part B will occur on the same day as Week 48 visit of Part A, and patients should complete all Part A Week 48 assessments before signing the informed consent for Part B. Informed consent for Part B will be signed before any Part B specific assessments are performed. In the event that a patient has their baseline visit of Part B after the Part A Week 48 visit (but within the █ window), they will NOT have to repeat any Part B assessments that were specified to be performed at the Week 48 visit of Part A.

^b The █ safety follow-up will be required for all patients who discontinue study treatment early. This assessment may be performed as a phone call, unless ongoing clinical laboratory findings or adverse events require additional follow-up.

^c Unscheduled visits may be performed if clinically indicated.

^d Weight and height will be measured with shoes off and preferably with the same balance at each visit.

^e Vital signs (pulse rate, respiration rate, blood pressure, and temperature) will be collected after the patient has been seated or recumbent for at least 5 minutes and before any 12-lead ECG assessment or blood sampling is performed.

^f Twelve-lead ECGs will be performed after patients have been recumbent for at least 5 minutes, after the measurement of vital signs, and before any procedures that may affect heart rate (eg, blood sampling).

^g Twelve-lead ECGs will be performed annually after █ (ie, only at █)

^h Physical examinations include an evaluation of body systems, including but not limited to the following: skin; head, eyes, ears, nose, and throat; respiratory system; cardiovascular system; abdomen (liver, spleen); lymph nodes; neurological system; and musculoskeletal system.

ⁱ Urine pregnancy tests will be performed for all female patients of childbearing potential before dispensation of study drug at all other visits. If pregnancy is found, patients must be terminated from the study effective immediately. Home pregnancy tests will be performed for all female subjects of child-bearing potential if required per local regulations.

^j For baseline visit, patients will be required to fast for at least 4 hours prior to laboratory blood samples being taken.

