9.3.1.4 On-treatment

For patients that do not prematurely discontinue treatment, all post-baseline measurements on or before the end of the Week 48 window are considered on-treatment.

For patients that do prematurely discontinue treatment, only measurements that are taken whilst a patient is taking the study treatment will be on-treatment measurements. More specifically if:

$$(\text{Assessment date}) - (\text{Date of first dose}) + 1 > 0; \text{ and} \\ (\text{Date of last dose}) + 2 - (\text{Assessment date}) \geq 0$$

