9.3.4 Safety derivations

9.3.4.1 Adverse events

Adverse events (AEs) and serious adverse events (SAEs) will be collected from the time of signature of the informed consent form (ICF), until after either the 7-Day follow-up period is completed or up to 30 days after the patient has stopped study treatment, whichever is later.

All AEs and SAEs are recorded in the Adverse Event Form.

A treatment-emergent AE (TEAE) is defined as an AE that meets any of the following conditions:

- begins on or after the first dose of study drug and on or before the stop of study drug + 35 days
- begins before the first dose of study drug and worsens on or after the first dose of study drug and on or before the stop of study drug + 35 days
- is completely missing an onset date and end date
- is completely missing an onset date and the end date is on or after the first dose of study drug and on or before the stop of study drug + 35 days.

REACH TRIAL

Stop of study drug is recorded in the End of Treatment form as the Date of Last Dose.

Missing start and stop dates for TEAEs will be handled as follows:

- ??-MMM-YYYY: If the AE month and year are different from the month and year of the first dose of study drug, assume 01-MMM-YYYY. If the month and year are the same as the first dose of study drug month and year and the AE end date (after any imputation) is on or after the first dose of study drug, then assume the date of the first dose of study drug. If the AE month and year are the same as the first dose of study drug month and year and the AE end date (after any imputation) is prior to the first dose of study drug, then assume the end date for the onset date.
- DD-???-YYYY/??-??-YYYY: If the AE year is different from the year of first dose of study drug, assume DD-JAN-YYYY/01-JAN-YYYY of the collected year. If the AE year is the same as the first dose of study drug year (and in the case of AEs that are non ongoing the AE end date (after any imputation)) is on or after the first dose of study drug, then assume the date of the first dose of study drug. If the year is the same as the first dose of study drug and the AE end date (after any imputation) is prior to the first dose of study drug, then assume the end date for the onset date.

Missing end dates:

- ??-MMM-YYYY: Assume the last day of the month
- DD-???-YYYY: Assume DD-DEC-YYYY
- ??-???-YYYY: Assume 31-DEC-YYYY.

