9.5 ASSESSMENT TIME WINDOWS

9.5.1 Definition of permissible time windows

All study visits from baseline to Week 48 have a window of +/- 7 days inclusive in the schedule of assessments. For the purpose of efficacy, PK and safety analysis, visit windows will be treated as continuous, from the midpoint between two consecutive study visits:

Visit	Window
Screening	From enrollment to randomization

REACH TRIAL

Baseline	Day of randomization, or date of last non-missing value obtained prior to the first dose of study treatment.
Week 4	Days 15 to 56
Week 12	Days 57 to 126
Week 24	Days 127 to 210
Week 36	Days 211 to 294
Week 48	Days 295 to the earliest of Day 357 or Day of OLE Study Drug Dose 1

Data collected after the first dose of study treatment up to and including Day 14 will be treated as unscheduled. Where there is more than one measurement within a visit window, the visit closest to the target visit date will be included for analysis. Where two visits are equidistant to the target visit date, the later visit will be included for analysis. Data collected during visits that are excluded because another is closer to the target visit date will be treated as out-of-window observations.

Efficacy and PK data from both scheduled and unscheduled visits and from Early Termination visit will go through the above windowing process. Similarly, safety data from scheduled visits, from Early Termination visit and from Safety Follow-up visit will go through the above windowing process.

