10.3.2 Deaths and serious adverse events

The number and percentage of patients with at least one SAE in the following categories will be presented:

- Any SAE
- SAE related to study drug

The number of SAEs will be presented by treatment group. Numbers and percentages of patients with at least one SAE will be summarized by SOC and PT. All SAEs will be listed in the same way as AEs.

Deaths will be listed by FSHD type and treatment group, and include date of death, primary cause of death, relatedness and whether an autopsy was performed.

10.3.3 Adverse events leading to discontinuation of investigational product and/or withdrawal from the study

The number of TEAEs leading to discontinuation of study drug will be presented by treatment group. Numbers and percentages of patients with at least one TEAE leading to study drug discontinuation will be summarized by SOC and PT, and also by maximum CTCAE grade.

The number of TEAEs leading to withdrawal from the study will be presented by treatment group. Numbers and percentages of patients with at least one TEAE leading to withdrawal from the study will be summarized by SOC and PT, and also by maximum CTCAE grade.

All AEs leading to discontinuation of study drug will be listed in a single listing, in the same way as AEs. AEs leading to withdrawal from study are flagged in the AE listing.

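### The Part A TEAE window in SAP 9.3.4.1 runs to last dose + 35 days with no stop at the first open-label dose, so early open-label losmapimod events count as Part A TEAEs

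*SAP*

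**What the plan says.** SAP 9.3.4.1 gives four conditions for a TEAE. The first is that the event "begins on or after the first dose of study drug and on or before the stop of study drug + 35 days". The second (worsening of an earlier event) and the fourth (onset date missing, end date known) close at the same point. The third (both dates missing) has no time limit. The stop of study drug is the last-dose date on the End of Treatment form; the SAP does not say whether that is the Part A or the Part B date for a patient who continues.

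On the move to Part B, Protocol Table 8, note a, states: "In most cases, the baseline visit of Part B will occur on the same day as Week 48 visit of Part A". Protocol 3.1.2 adds: "During Part B, all patients will receive 15 mg PO losmapimod tablets BID with food".

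On the intended scope, Protocol 9.1.6.7 says: "Safety data in the placebo-controlled treatment period will be analyzed using the safety analysis set and summarized by treatment group". Protocol 3.1.1 says: "For patients who rollover into Part B, the Week 48 visit will be the end of study visit for Part A".

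The SAP does use the first open-label dose as a boundary in one place. SAP 9.5.1 defines the Week 48 window as "Days 295 to the earliest of Day 357 or Day of OLE Study Drug Dose 1". SAP 9.3.1.4 takes this over for patients who complete treatment, for whom "all post-baseline measurements on or before the end of the Week 48 window are considered on-treatment".

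**The concern.** For a patient who rolls over without a break, the 35 days after the last Part A dose are the first 35 days of open-label losmapimod. For a former placebo patient this is first exposure to the drug, and the TEAE rule attributes it to Part A. The cut at the first open-label dose in SAP 9.5.1 governs measurements taken at visits; adverse event onset dates do not go through visit windows.

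What is at stake is the Part A safety comparison, which is a secondary objective. Losmapimod events counted under placebo pull the two columns together. The effect is greatest for reactions that cluster at treatment start and for rare events. Protocol 1.3.2.1 shows how small the relevant counts can be: in ReDUX4, adverse events of raised ALT occurred in 2 of 40 losmapimod patients and 0 of 40 placebo patients. At that level one or two misassigned events change the picture.

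**Working it through.** **Where a cut-off exists and where it does not**

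- By-visit summaries: cut at the first open-label dose through SAP 9.5.1.
- On-treatment vital signs and QTcF: cut through SAP 9.3.1.4.
- TEAEs (9.3.4.1, 10.3.1): no cut.
- SAEs (10.3.2): "The number and percentage of patients with at least one SAE in the following categories will be presented", with no date limit.
- Overall AESI count (9.3.4.1, 10.3.4): derived from liver tests, with no date limit.
- Lowest and highest post-baseline laboratory shifts (10.3.5): no date limit, and they accept unscheduled and out-of-window values (9.5.2, 10.3).

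**Inputs**

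- Planned treatment: 335 + 1 = 336 days (SAP 8.3.1; Week 48 is Study Day 336).
- TEAE tail: 35 days (SAP 9.3.4.1).
- Placebo group: about 115 patients (SAP 3.1).
- Rollover share *r*: not in the documents; assumed 80% to 100%.
- Gap *g* (drug-free days between the last Part A dose and the first open-label dose): Table 8 implies about zero in most cases; 0 and 7 are used here.
- Open-label days inside the window: *d* = 35 − *g*. A switch within the same calendar day adds one day if the switch day is counted.

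**Share of one patient's window**

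Window length = 336 + 35 = 371 days.

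- *g* = 0: 35/371 = 9.4%
- *g* = 7: 28/371 = 7.5%
- *g* of 35 or more: 0

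**Exposure placed in the placebo column** = 115 × *r* × *d*, against a total placebo window of 115 × 371 = 42,665 days

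- *r* = 1, *g* = 0: 115 × 35 = 4,025 patient-days; 4,025/365.25 = 11.0 patient-years; 4,025/42,665 = 9.4%
- *r* = 0.8, *g* = 7: 92 × 28 = 2,576 patient-days; 2,576/365.25 = 7.1 patient-years; 2,576/42,665 = 6.0%

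These figures assume the full tail is in the data for everyone.

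**Two illustrations with assumed event rates**

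1. A reaction with no background rate affects 5% of new starters, evenly over their first 35 days. The true contrast is 5.0% vs 0%. Placebo as shown = 5.0 × *r* × *d*/35:
   - *r* = 1, *d* = 35: 5.0%, so the table reads 5.0% vs 5.0%
   - *r* = 0.8, *d* = 28: 5.0 × 0.8 × 28/35 = 3.2%, so the table reads 5.0% vs 3.2%
2. Any TEAE, with a placebo risk of 80.0% over 371 days and a rate that doubles on losmapimod. Daily rate *h* = −ln(0.20)/371. Placebo as shown = (1 − *r*) × 0.80 + *r* × [1 − exp(−*h*(371 + *d*))]:
   - *r* = 1, *d* = 35: 82.8%
   - *r* = 0.8, *d* = 28: 81.8%

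**Partial dates.** The SAP's imputation looks only at the first dose of study drug. If the onset month is known and is not the month of that dose, the first of the month is assumed. An open-label event in the rollover month with an unknown day can therefore be moved back before the first Part B dose.

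**After the change.** With the window closed at the first open-label dose, open-label days inside it are 0 for every gap. Patients who do not roll over keep all 35 days.

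**The case against.** The strongest reply is that the scope of the SAP already excludes these events. SAP 1 confines the plan to Part A, SAP 4.2 runs it on locked Part A data, and SAP 11 declares no departure from a protocol that analyses the placebo-controlled period. Protocol 6.1.4 distinguishes events occurring during Part A, and Table 8 gives Part B its own consent and its own adverse event row. On this view the 35-day tail was written for patients who stop treatment, and only a clause for rollovers is missing. This evidence of intent is good, but none of it is a date rule for adverse events, whereas SAP 9.3.4.1 gives an explicit one. Nor do the documents show that Part B events are kept out of the data: Protocol 7 has events recorded through the last Part A or Part B visit, and Protocol 6 keeps the same patient number. By the time of analysis, earlier rollovers will have open-label follow-up.

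A second reply is that the placebo column is affected only if the safety set is read as in Protocol 9.1.4. SAP 6.2 omits the restriction to the placebo-controlled period and assigns anyone who receives both treatments to losmapimod. Read literally, it would move rolled-over placebo patients to the losmapimod group. That is correct, but this reading also misassigns events. The protocol defines the safety set explicitly and gives no closing date for TEAEs, so reading SAP 6.2 in its light is reasonable.

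Three further points stand. The rollover shares and event rates are assumptions, and late rollovers may lack a full tail at database lock. The laboratory and AESI outputs are a weaker case, because nothing classes scheduled Part B visits as unscheduled or out-of-window. The listings will show onset dates and TEAE flags, so misassigned events could be traced afterwards.

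**Conclusion.** The concern holds. As written, SAP 9.3.4.1 counts open-label losmapimod events as Part A TEAEs, against the protocol's evident intent. With the safety set read as in Protocol 9.1.4, 6.0% to 9.4% of the placebo group's TEAE window would be losmapimod exposure under the assumed rollover and gap. The distortion is small for common events (1.8 to 2.8 points in the any-TEAE illustration). It can be large for a reaction at treatment start: the difference shown falls to between 0 and 1.8 points against a true 5.0.

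The actual size cannot be fixed from the documents, and contamination is not certain, because they do not say whether Part A and Part B adverse event records are separated. The overlap would be longer if the recorded stop of study drug were the Part B date. The SAE, AESI and laboratory outputs are secondary; the conclusion does not depend on them. The point should be fixed before unblinding, but it does not bear on the efficacy conclusions.

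**What to change.** - **SAP 9.3.4.1:** close the TEAE window, in both groups, at the earlier of last Part A dose + 35 days and the first Part B dose. State that the stop of study drug means the last Part A dose.
- **Same-day onset:** state how an event starting on the day of the first Part B dose is assigned, for example by onset time (which Protocol 7.3.1 lists for collection), with a default when the time is missing.
- **Partial or missing onset dates:** add a default around the first Part B dose, covering the condition in which both dates are missing.
- **Other outputs:** apply the same cut-off to the SAE summaries (10.3.2), the AESI count (9.3.4.1, 10.3.4) and the lowest/highest laboratory shifts (9.5.2, 10.3.5).
- **SAP 6.2:** restore the protocol's restriction to the placebo-controlled period, and limit the rule for patients who receive both treatments to drug received in Part A.

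The cost is a few clauses in the SAP. The first open-label dose date is already used in SAP 9.5.1, and no new data are needed.

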7.1.2. Definition of Treatment-Emergent Adverse Event

A TEAE is defined as any event that was not present before exposure to the study drug or any event already present that worsens in either intensity or frequency after exposure to the study drug.

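### The SAP applies its 35-day limit to the end date of adverse events with unknown onset, so those that resolve late drop out of the TEAE tables

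*SAP*

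**What the plan says.** SAP 9.3.4.1 gives four routes to treatment emergence:

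- Condition 1 uses onset: the event "begins on or after the first dose of study drug and on or before the stop of study drug + 35 days".
- Condition 2 applies the same window to the worsening of an event that began before treatment.
- Condition 3 admits an event that "is completely missing an onset date and end date".
- Condition 4 admits an event that "is completely missing an onset date and the end date is on or after the first dose of study drug and on or before" stop of study drug plus 35 days.

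The section then imputes partial onset dates. If only the day is missing, and the month is that of first dose, one branch opens "If the month and year are the same as the first dose of study drug month and year and the AE end date" and requires that end date to fall on or after first dose. The other branch requires it to fall before. The next rule, for a missing month, restricts the end-date test: "in the case of AEs that are non ongoing the AE end date".

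Partial end dates are moved to the latest date compatible with what was recorded, capped at study cutoff or death. Nothing is imputed for an event with no end date. SAP 9.3.1.3 leaves AE dates to this section, so its visit-date fallback does not apply.

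Protocol 7.1.2 looks at appearance or worsening: "A TEAE is defined as any event that was not present before exposure to the study drug", or one that worsened after exposure.

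**The concern.** The lower bound in condition 4 is sound, because an event that ended before first dose must have begun before it. The upper bound has no such logic. An event that ends long after treatment may have begun on any day of treatment.

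Condition 3 makes the rule inconsistent as well. An unknown-onset event counts while its end date is blank and can stop counting once a late resolution date is entered.

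Elsewhere the SAP settles doubt towards the drug: both dates missing counts as treatment-emergent, onset in the first-dose month defaults to the first-dose date, and missing relatedness is taken as related. Condition 4 goes the other way, for events that persisted. The outputs exposed are the TEAE tables in SAP 10.3.1 and the tables of TEAEs leading to drug discontinuation or study withdrawal in 10.3.3.

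The month-and-year rule raises a smaller matter. Both of its first-dose-month branches need an end date, and an ongoing event has none.

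**Working it through.** The plan states no figure to reproduce, so the check is to apply the rules literally to specimen records. All dates below are hypothetical.

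**Unknown onset.** First dose is Day 1. The limit is the stop day plus 35, so a stop on Day 336 gives 336 + 35 = Day 371, and a stop on Day 60 gives 60 + 35 = Day 95.

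| Stop | End date | Rule | Result |
|---|---|---|---|
| Day 336 | Day 300 | condition 4, 300 ≤ 371 | TEAE |
| Day 336 | Day 371 | condition 4, at the limit | TEAE |
| Day 336 | Day 372 | condition 4 fails | not TEAE |
| Day 336 | Day 400 | condition 4 fails | not TEAE |
| Day 336 | none | condition 3 | TEAE |
| Day 60 | Day 110 | condition 4 fails, 110 > 95 | not TEAE |

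**Imputed end dates.** Take first dose 15 March 2023 and last dose 335 days later, 13 February 2024. The limit is 19 March 2024.

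- An end recorded as `??-MAR-2024` becomes 31 March 2024, which is 12 days past the limit, so the event is not a TEAE. The true end could have been on or before 19 March.
- An end recorded only as 2024 becomes 31 December 2024, capped at an assumed cutoff of 30 September 2024. It is also past the limit, so not a TEAE.

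Imputing the end late can therefore remove the event by itself.

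**Onset known to month and year.** Same patient.

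| Onset | End date | Imputed onset | Result |
|---|---|---|---|
| `??-MAR-2023` | Day 10 | first dose | TEAE |
| `??-MAR-2023` | stop + 120 days | first dose | TEAE |
| `??-MAR-2023` | ongoing | none | undefined |
| `??-APR-2023` | ongoing | 1 April 2023 | TEAE |
| year 2023 only | ongoing | first dose | TEAE |
| day and year 2023 | ongoing | first dose | TEAE |

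The second row shows that a late end date does no harm once the month of onset is known. The third row is the gap. Condition 3 cannot rescue it, because its onset is not completely missing. The last two rows read the year rule as it is evidently meant, with the end-date test applied only to events that have ended.

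**Size.** The documents give no rate of incomplete AE dates, and the first pattern cannot be quantified. For the second, assume that 1% to 5% of events lack the onset day, 10% of those fall in the first-dose month, and 25% of those are ongoing. That gives 0.01 × 0.10 × 0.25 = 0.025% to 0.05 × 0.10 × 0.25 = 0.125% of events. All three rates are assumptions.

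**The case against.** **The patterns are rare.** Protocol 7.3.1 requires time of onset, and 6.1.4 has events elicited at every visit. The first pattern needs an event with no onset information at all, not even a year, plus an end date past the limit. A reader might infer that the rules fail for long-lasting events in general. They do not. Any event with a full onset date is classified by that date whatever its duration, unknown-onset events without an end date count under condition 3, and most ongoing events with partial onset are handled. This objection stands and limits the size of the point.

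**Late end dates may be uncommon outside Part B.** For a completer who does not roll over, the last contact is the phone screen at Day 373 ± 5, about stop + 37, and Protocol 7.4 ends follow-up at completion of participation. However, Protocol 6.1.4 and 7.3.1 speak of following events to resolution, and patients who stop drug early are encouraged to stay in the study (4.3.2). Late end dates cannot be ruled out.

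**The limit may guard against Part B events.** Part B dosing can start on the day of the Week 48 visit, and ongoing events are followed into Part B. An unknown-onset event that ends months later might have begun on open-label losmapimod. Deleting the limit outright could charge such an event to the Part A arm, including placebo, which would shrink a difference between arms. The SAP does not give this reason and condition 3 has no such limit, but the risk is real and the fix must deal with it.

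**The protocol definition is weak support.** Protocol 7.1.2 sets no window at all, so it cannot settle where one should end. It shows only that onset and worsening matter, not resolution.

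**The ongoing event has an obvious intended reading.** A reader might infer that an ongoing event dated to the first-dose month is excluded as non-emergent. The text does not say so. It leaves the onset unassigned. An ongoing event cannot have ended before first dose, so the first branch is the natural reading, and a programmer would probably follow the neighbouring year rule. Misclassification is not shown; this is a clarification only.

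**Conclusion.** The point on condition 4 holds. It is a stated rule that classifies the same event differently according to when, or whether, an end date is recorded, and it excludes late-resolving events on a ground unrelated to onset. The ongoing-event gap in the month-and-year rule is real but minor, because the status is undefined rather than wrong.

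The effect is small. It is confined to two date patterns and probably to few events, though this cannot be confirmed without a rate of incomplete dates. No difference between arms is shown. Efficacy analyses and the type I error are untouched. The SAE tables in SAP 10.3.2 are not restricted to TEAEs, and every AE is still listed under 10.3.1, where only the TEAE flag could change.

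The conclusion rests on a literal reading of SAP 9.3.4.1, with no programming convention outside the SAP filling either gap.

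**What to change.** **Condition 4.** Count an event with completely missing onset as treatment-emergent when its end date is on or after first dose, and delete the upper limit on the end date. Add one exception: if the event was first reported after the first Part B dose, assign it to Part B.

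**Month-and-year rule, first-dose month (clarification).** In the first branch, insert *the AE is ongoing or* before "the AE end date (after any imputation) is on or after the first dose of study drug". An ongoing event then takes the first-dose date as its onset, as the year rule already provides.

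**Cost.** Two short edits to the SAP and the matching program lines, with no new assessments. They are best made before unblinding, so that nobody has to choose a rule with the treatment codes in view. The downside is that an occasional unknown-onset event that truly began after the window will count as a TEAE. This could happen, for example, in a patient who stopped drug early, stayed in the study and had a later event recorded without any onset date.
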